Hypothesis: TKA will impair whole body and muscle function, in part, through reductions in skeletal muscle fiber size, with preferential atrophy in MHC II sub-types, reduced single fiber tension (force/CSA) and velocity and decreased mitochondrial content and function.

Aim 2: Define the utility of NMES to prevent early, postsurgical skeletal muscle structural and functional adaptations to TKA.

Hypothesis: NMES will lessen TKA-induced muscle fiber atrophy and contractile dysfunction and preserve or increase mitochondrial content and respiration while lessening mitochondrial ROS production.

METHODS AND PROCEDURES

We will use a randomized, controlled design, in which older adult patients with knee OA being evaluated for TKA will be recruited and undergo baseline evaluations (Pre-surgery Testing) prior to surgery. Patients will then be randomized (1:1) to a 5 week intervention of NMES or control (n=32/group, expecting 25% attrition rate to arrive at n=24/group) using a covariate-adaptive approach, which will incorporate age, BMI, sex and surgeon into the randomization scheme. After completing the intervention, they will be re-tested at 5 weeks (5 wk Post-surgery Testing) following surgery. Volunteers can opt into an optional 2 week follow-up testing period. Primary outcomes will be tested at the 5 week evaluation, with 2 wk testing including assessment of ancillary mechanistic hypotheses. Assessment of physical activity by accelerometry (5 d each throughout the 5 week post-surgical period) will monitor variation in physical activity between groups. Each phase of the protocol is described below.

Pre-surgery testing will include assessments of whole muscle size and function, accelerometry to assess habitual weight-bearing activity level, single muscle fiber size and mechanical function and mitochondrial content and function. Detailed descriptions of these assessments are provided below.

Treatment intervention Volunteers will be randomized to NMES or control groups for the 5 weeks following TKA surgery (described below in detail).

5 wk Post-surgery testing will include measurements identical to Baseline Testing, with post-training biopsies performed ≥ 3 d following strength testing/NMES to eliminate any residual effects, per our usual protocol in our past IRB-approved training studies in other clinical populations (heart failure, end-stage knee osteoarthritis).

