Statistical Analytical Plan

Project Title:

Skeletal muscle atrophy and dysfunction following total knee arthroplasty

Version Date:

3-23-22

NCT number:

NCT03051984

**Principal
Investigator
(contact):**

[name]

Grant Sponsor:

NIA R01 AG050305

For Aim 1, using pre-surgery and 5 wk post-TKA assessments in the control group, we will assess the effect of TKA (pre- vs. 5 wk post-TKA) on muscle fiber size and function. Primary outcomes include: single muscle fiber CSA for MHC I and IIA fibers and tension and velocity for MHC I and IIA fibers, and IMF and SS mitochondrial content. We will use a general linear mixed model, with a random effect to account for observations clustered within patients (eg, single fiber CSA and function), with the model conceptualized as a multi-level analysis with single fiber values comprising level 1 variables and whole muscle or person-level covariates comprising level 2 variables (130). Covariates (eg, baseline value, etc.) can be included in the model as level 2 variables to determine if variation in any primary outcome is related to variability in these factors. Additionally, we can include sex in the model to examine whether the effects of TKA differ between men and women. In secondary analyses, we will examine whether changes in muscle fiber size or functional mediate changes in whole muscle and body function using mediation analysis, if effects of TKA are noted in the latter. Such analyses seeks to determine whether the effect of an independent variable or intervention (TKA) on some outcome variable (whole muscle/body function) can be transmitted through a third variable, referred to as a mediator (single fiber CSA or function). Variables with multiple observations per subject will be collapsed into a single mean value.

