For Aim 2, pre- and 5 wk post-surgery data will be compared between volunteers randomized to NMES and control interventions. Our primary analysis will assess treatment effects (group X time interaction) on muscle structural and functional variables. Primary outcomes are identical to Aim 1 and will be similarly evaluated using a general linear mixed model, as described above, with group (NMES vs. control) and time (pre vs. 5wks post-TKA) as between- and within-subject factors, respectively. Potential confounding factors will be compared between groups and factors that differ can be included into the model as level 2 covariates. We assume that dropouts will be random, but will examine whether they differ from volunteers completing the study. Moreover, we can conduct sensitivity analysis on dropouts, assuming the most and least conservative responses, to assess their impact on study outcomes. Additionally, we can include sex as an additional effect in these models to determine if NMES effects differ by sex. In secondary analyses, we will also examine the effect of treatment on whole muscle/body functional measures. If there are effects of NMES to maintain whole muscle/body functionality at 5 weeks, we will examine whether changes in single fiber structural or functional outcomes partially or completely mediate whole muscle/body functional improvements with NMES using mediation analysis.

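### The Aim 2 primary test, a group × time interaction with a separate baseline mean in each arm, is valid on patient means but usually less precise than a comparison adjusted for the pre-randomisation baseline

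*SAP*

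**What the plan says.** The Aim 2 paragraph of the SAP sets the primary test: "Our primary analysis will assess treatment effects (group X time interaction) on muscle structural and functional variables". The outcomes "will be similarly evaluated using a general linear mixed model, as described above, with group (NMES vs. control) and time" as the two factors, time having two levels (pre-surgery and 5 weeks). The pre-surgery value is therefore an outcome row, and each arm has its own baseline mean.

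The model itself is described under Aim 1. It is fitted "with a random effect to account for observations clustered within patients", "with the model conceptualized as a multi-level analysis with single fiber values comprising level 1 variables". The list reads "Primary outcomes include: single muscle fiber CSA for MHC I and IIA fibers and tension and velocity for MHC I and IIA fibers", to which the SAP adds two mitochondrial content measures. That makes eight primary outcomes, six of them single-fibre.

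Three other statements bear on the point:

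- The Aim 1 text allows an optional adjustment: "Covariates (eg, baseline value, etc.) can be included in the model as level 2 variables". Its stated purpose is to explore sources of variation in the outcomes.
- The Aim 1 mediation text ends: "Variables with multiple observations per subject will be collapsed into a single mean value". This is not said of the Aim 2 primary model.
- The Protocol, Methods and Procedures, says that patients "undergo baseline evaluations (Pre-surgery Testing) prior to surgery. Patients will then be randomized (1:1", with 32 per group expected to yield 24 per group.

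Neither document specifies a common baseline mean for the two arms, or a 5-week comparison adjusted for baseline.

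**The concern.** Baseline is measured before allocation, so treatment cannot have changed it and the expected difference between arms at that visit is zero. The planned model estimates that difference anyway, and the interaction carries its sampling noise. In effect it removes the whole observed baseline difference, whatever the actual relation between the pre-surgery and 5-week values.

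At stake is precision. With about 24 completers per group, an interval wider than it needs to be matters, and a narrower one requires no further data.

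**Working it through.** **1. The plan's own figure.** 24/(1 − 0.25) = 32 per group, as stated. Alpha, power, effect size, SDs and the pre/post correlation are not given, so the power behind 24 cannot be reproduced. All r and k below are assumed, and tests are taken as two-sided at 0.05.

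**2. Variances on patient means.** Set the baseline SD to 1 and the 5-week SD to k. Each variance below is multiplied by 2/n, with n patients per arm.

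- Interaction (difference in mean change): 1 + k² − 2rk.
- Baseline-adjusted: V = k²(1 − r²).
- Difference: 1 − 2rk + r²k² = (1 − rk)². This is never negative, and is zero only at rk = 1.

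Two examples. At k = 1, r = 0.5: 0.75/1.00 = 0.75. At k = 1.3, r = 0.7: 0.862/0.870 = 0.99.

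| Variance, adjusted ÷ interaction | r = 0.3 | 0.5 | 0.7 | 0.9 |
|---|---|---|---|---|
| k = 0.7 | 0.42 | 0.47 | 0.49 | 0.40 |
| k = 1 | 0.65 | 0.75 | 0.85 | 0.95 |
| k = 1.3 | 0.81 | 0.91 | 0.99 | 0.92 |
| k = 1, slope estimated, 24/group (simulated) | 0.66 | 0.77 | 0.87 | 0.97 |
| k = 1.3, slope estimated, 24/group (simulated) | 0.82 | 0.93 | 1.02 | 0.93 |
| k = 1, 32 baselines and 24 completers per group | 0.71 | 0.80 | 0.88 | 0.96 |
| k = 1.3, 32 baselines and 24 completers per group | 0.85 | 0.93 | 0.99 | 0.94 |

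Estimating the slope with 48 patients multiplies the adjusted variance by about 1 + 1/44 = 1.023. The last two rows let the planned mixed model keep the 32 − 24 = 8 baseline-only patients per group, with dropout at random. The interaction variance becomes V + (24/32)(1 − rk)², so the ratio is V/(V + 0.75(1 − rk)²).

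**3. Validity.** In simulation on patient means (12 settings, 40,000 trials each), type I error was 4.9 to 5.1% for the interaction and for ANCOVA alike.

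**4. In terms of power.** Take a difference of 0.826 SD of change, which gives the interaction 80% power at 24 per group. For r = 0.3, 0.5, 0.7, 0.9, the adjusted analysis then has 93, 89, 85 and 81% at k = 1, and 87, 83, 79 and 82% at k = 1.3.

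**5. The optional baseline covariate.** A person-level covariate adds the same amount to a patient's pre-surgery and 5-week rows, so it cancels from the change. With balanced data the interaction estimate does not move; this was confirmed in three of three test data sets. In another simulated data set the estimate was 0.1633 with and without the covariate, yet the model's standard error fell from 0.252 to 0.234. That gain is not real.

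**6. A common baseline mean with equal variances forced.** A random-intercept model then uses the slope b = 2rk/(1 + k²), and the variance is k² + b² − 2brk. At k = 1.3, r = 0.9: b = 2.34/2.69 = 0.870, variance 1.690 + 0.757 − 2.036 = 0.411, against 0.350 for the interaction, a ratio of 1.17. For r = 0.3, 0.5, 0.7 the ratios are 0.81, 0.93, 1.05. In simulation at k = 1.3 (3,000 trials per cell), the model's standard error was 0.88 to 0.89 of the true one and type I error was 7.7 to 8.5%. At k = 0.7 type I error was 1.6 to 1.9%.

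**The case against.** The difference in change is a standard, unbiased analysis, and the plan does use baseline, as the pre-surgery row. A reader might infer that the planned test is biased or ignores baseline; the documents support neither. What remains is a loss of precision of unknown size, which is close to nil when rk is near 1. In the worst case tabulated, ANCOVA costs about 2% of variance.

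The SAP's permission to include baseline value might seem to settle the matter. It does not. It is optional, it sits under Aim 1, and it leaves the interaction unchanged in balanced data. With dropout or uneven fibre counts the estimate shifts slightly, without useful gain.

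The strongest objection concerns scope. For six of the eight primary outcomes, the text reads most naturally as fibre-level rows with a patient effect only. A reader might infer that the planned intervals for those outcomes are also too wide, or that this point vouches for that model. Neither follows. With no patient-by-visit term, the reported standard error can be too small. That is a separate issue and is not assessed here. This objection stands as a limit on the claim.

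It is also fair to say that a careless remedy could do harm: a common-baseline model that forces equal variances can be worse than the plan when k exceeds 1 (step 6). The fix is worded to prevent this.

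**Conclusion.** The point holds as one of efficiency. If Aim 2 is analysed on patient means or with a patient-by-visit effect, the planned interaction is valid but usually less precise than an analysis with baseline as a covariate or with a common baseline mean. For r from 0.3 to 0.9 the variance saving is 5 to 35% at k = 1, 1 to 19% at k = 1.3 and 51 to 60% at k = 0.7, before the slope cost. At k = 1 it falls to 4 to 29% if the mixed model keeps baseline-only patients.

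These figures rest on assumed r and k, on 24 completers per group, and on dropout at random, which the SAP itself assumes. A reader might infer from the power figures that the trial is underpowered. The documents give no power calculation, and the 80% starting point is only a reference, so that inference is not supported. The change is worth making because it is cheap; the plan is not invalid without it.

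**What to change.** In the Aim 2 text of the SAP, name as primary an ANCOVA of each patient's 5-week mean on that patient's own pre-surgery mean for the same outcome. It costs one degree of freedom, moves the fibre outcomes from the multilevel model to patient means (a summary the SAP already uses for mediation), and drops patients who have baseline data only.

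The alternative, which keeps those patients, is a longitudinal model of both visits with a common baseline mean in the two arms. It must allow different variances at the two visits. For fibre-level rows it must also include a patient-by-visit random effect alongside the patient effect.

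In either case, state that baseline value is not entered as a covariate in any model where the pre-surgery value is also an outcome row. The change is to SAP wording and needs no new data.

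### The Aim 2 primary model does not commit to the four factors that govern allocation, and the rule for adding covariates would seldom select them or change the group x time estimate

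*SAP*

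**What the plan says.** The Protocol (Methods and Procedures) randomises 1:1 "using a covariate-adaptive approach, which will incorporate age, BMI, sex and surgeon into the randomization scheme". It plans 32 patients per group, "expecting 25% attrition rate to arrive at n=24/group".

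The SAP paragraph on Aim 2 makes the group x time interaction the primary test, in a mixed model "with group (NMES vs. control) and time (pre vs. 5wks post-TKA) as between- and within-subject factors". The random part is carried over from Aim 1, where the model is fitted "with a random effect to account for observations clustered within patients" and single-fibre values form level 1.

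On covariates, the SAP says:
- Aim 2: "Potential confounding factors will be compared between groups and factors that differ can be included into the model as level 2 covariates".
- Aim 1, the model that Aim 2 refers back to: "Covariates (eg, baseline value, etc.) can be included in the model as level 2 variables". Baseline value is the only example given.
- Sex, Aim 2: "we can include sex as an additional effect in these models to determine if NMES effects differ by sex".

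Age, BMI and surgeon are not named in the SAP. It gives no criterion for a difference between groups, no coding, and no choice between a main effect and a covariate x time term.

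**The concern.** Factors used to constrain allocation normally go into the primary model. The scheme removes part of their contribution to the variation between arms, and an analysis that ignores them leaves that contribution in its standard error. Here none of the four has a committed place. The rule that might bring them in depends on the observed data and looks for imbalance, which the allocation is built to prevent.

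Even when the rule does select a factor, a person-level main effect mainly describes level, while the primary test concerns change. An analyst could follow the SAP, report an adjusted result, and have almost the unadjusted one. At stake are some precision with 24 analysed per group, and a choice of model left open after the data are seen, across eight primary outcomes.

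**Working it through.** **Plan's own figure.** 24/(1 − 0.25) = 32 per group, which reproduces. The 24 cannot be derived, because no alpha, power, effect size or SD is given.

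**Assumed inputs (not in the documents).** Biased-coin minimisation with probability 0.8; age and BMI split at the median; three surgeons; 64 allocated with random loss to 48; two-sided 5% test. R2 is the share of variance in change explained by the four factors together, split equally between them.

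**1. How often the rule selects a factor.** At least one of the four differs at p<0.05 in 2.2% of simulated trials (1.4 to 3.5% over coin 0.7 to 1.0 and two to six surgeons). Repeats with similar settings gave about 8% at p<0.10 and 22 to 24% at p<0.20. With dropout related to age and BMI in one arm only (assumed log-odds of 1 per SD), the p<0.05 figure was 12%.

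**2. Form of entry.** One simulated complete data set had 48 patients and 10 fibres per visit:

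| Terms | group x time | SE |
|---|---|---|
| group, time, group x time | 0.62387 | 0.13111 |
| + age main effect | 0.62387 | 0.13111 |
| + age and age x time | 0.67602 | 0.12906 |

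The main effect changes nothing. The age x time term moves the estimate by (0.67602 − 0.62387)/0.13111 = 0.40 SE. Age was built to differ between arms in this example, so it shows the mechanism and not a typical size.

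With 64 patients before and 48 after surgery, and a patient x time effect in the model, main effects shift the estimate by 0.06 to 0.07 SE on average (maximum 0.53; SE ratio 1.002 to 1.004). Covariate x time terms shift it by 0.17 to 0.29 SE (maximum 1.60).

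**3. Person-level means** (8,000 trials, standardised effect 0.826):

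| R2 | Type I, unadjusted % | Power, unadjusted % | Power, adjusted % | SE ratio |
|---|---|---|---|---|
| 0 | 5.0 | 80.0 | 77.5 | 1.03 |
| 0.05 | 4.7 | 79.9 | 79.5 | 1.00 |
| 0.1 | 4.5 | 80.3 | 81.8 | 0.98 |
| 0.2 | 4.1 | 80.8 | 86.1 | 0.92 |
| 0.3 | 3.5 | 81.2 | 90.3 | 0.86 |

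Adjusted type I error is 4.9%. The SE ratios follow 1.03 × √(1 − R2); for example, 1.03 × √0.7 = 0.86. Interpolating the power differences (−0.4 at 0.05, +1.5 at 0.1) puts break-even at 0.05 + 0.05 × 0.4/1.9 ≈ 0.06.

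**4. Fibre-level model with a patient x time effect** (4,000 trials per setting; 3 to 25 fibres per visit; fibre SD 1.5 or 3 times the SD of true change, all assumed). Change in power from adjusting, in points:

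| R2 of true change | Fibre SD 1.5 | Fibre SD 3 |
|---|---|---|
| 0 | −2.4 | −2.9 |
| 0.05 | −1.4 | −1.3 |
| 0.1 | +0.5 | −1.2 |
| 0.3 | +5.4 | +2.0 |

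Break-even is 0.05 + 0.05 × 1.4/1.9 ≈ 0.09 and 0.1 + 0.2 × 1.2/3.2 ≈ 0.18. Fibre sampling noise dilutes R2.

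**5. Fibre-level model with a patient intercept only.** The covariate x time SE ratio is 1.02 to 1.03. Null rejection is 12 to 33% unadjusted and 11 to 32% adjusted. This reading covers six of the eight primary outcomes: CSA, tension and velocity, each in MHC I and IIA fibres. The other two are IMF and SS mitochondrial content.

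**Monte Carlo error.** For a power difference near 80%, treating the two arms of the comparison as independent, it is √(2 × 0.8 × 0.2/8,000) = 0.6 points in step 3 and √(2 × 0.8 × 0.2/4,000) = 0.9 points in step 4. Differences of about one point should not be read closely.

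**The case against.** The strongest reply is that, on the most literal reading of the SAP, adjustment brings nothing. Aim 1 describes one random effect for patients over fibre-level data and Aim 2 inherits it; step 5 shows no gain there. The sentence "Variables with multiple observations per subject will be collapsed into a single mean value" does not clearly rescue the person-level reading, because it closes the description of the mediation analysis and most naturally belongs to it. This stands. The efficiency argument applies only to person-level means or to a model with a patient x time effect.

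It also stands that the gain depends on an undocumented R2 and can be a loss, and that how rarely the rule selects a factor depends on a criterion the SAP does not state. At a loose threshold, or with differential dropout, it would select one more often. Nor does the SAP exclude the four factors: its wording admits any potential confounder, and it does name sex.

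None of this supplies a commitment. Sex is named to study effect modification, not to reflect the allocation, and no reading of the rule says how a factor should enter.

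**Conclusion.** The point holds as a minor gap in pre-specification with a better method available at little cost. The absence of a committed list and form is plain from the documents. The size of the benefit is not.

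A reader might infer two stronger things that the documents do not support:
- **That omitting the factors produces false positives or invalidates the trial.** It does not. With person-level means, unadjusted type I error falls from 5.0% at R2 = 0 to 3.5% at R2 = 0.3, so the test is mildly conservative. The inflation in step 5 comes from the missing patient x time term, and adjusting for the four factors does not cure it.
- **That adjustment would raise power.** It does so only above an R2 of about 0.05 to 0.18, depending on the model and the fibre noise. R2 for change is not given, so no power gain should be presented as expected.

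All sizes rest on the assumed allocation algorithm, number of surgeons, fibre counts and variances.

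**What to change.** For the Aim 2 primary model, replace the rule about factors that differ with one fixed form, whatever the observed balance:
- Enter age and BMI (continuous), sex and surgeon, each with its covariate x time term. Pool surgeons, or treat surgeon as random, if there are many.
- Fit a mixed model with patient and patient x time random effects. The second is needed in its own right for fibre-level outcomes. Where there is one value per patient and visit, the residual plays that part.
- Report the model without the four factors as a sensitivity analysis. Keep the test of whether the NMES effect differs by sex as a separate secondary model.
- If outcome data have already been examined, say so and label the adjusted analysis accordingly.

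The cost is SAP wording and, with three surgeons assumed, 1 + 1 + 1 + 2 = 5 of 48 − 2 = 46 degrees of freedom. If the factors do not predict change, this costs about 2 to 3 power points (1.8 with two surgeons, 4.5 with six as fixed effects, hence pooling or a random effect). N stays at 32 per group, and all four variables are already collected for randomisation.
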